- **PRQ6** To explore data redundancy at the 6-month end point to provide information on outcome assessments.
- PRQ7 To explore what constitutes business as usual across the two sites, Bristol and Newport.
- **PRQ8** To qualitatively explore the feasibility, acceptability and barriers associated with referral pathways with a particular focus on equity, diversity and inclusion.
- **PRQ9** To qualitatively explore intervention delivery and outcome assessments from the perspectives of participants, their family, intervention providers and key stakeholders.
- **PRQ10** To explore the cultural sensitivity of the intervention and trial methods and explore whether further adaption to the intervention is necessary.
- **PRQ11** To explore whether MDFT has any iatrogenic or unintended consequences.

Design

The study protocol has undergone an independent equality impact assessment (EIA) (appendix III). The EIA explores equity, diversity, and inclusion from a variety of perspectives. The EIA was coproduced with a Young Persons Advisory Group (YPAG). The MDFT intervention will undergo an initial adaption stage, coproduced with an advisory group who are representative of the population where the intervention will be delivered.

Information sheets, privacy notices and consent forms are designed to be understood and completed by young people. All outcome measures are validated for the age of the target population. Experts in the design of research for young people with intellectual disabilities, SEND and neurodiversity will be consulted to ensure the materials align with best practice. Where necessary translated materials will be prepared to meet the needs of a diverse ethnic population and where translated versions are not available, translators, including British Sign Language will be made available. Initial assessment will be conducted in a variety of Barnardo's and community locations that are accessible irrespective of disability status and young people will be encouraged to choose a location they find most comfortable. Follow-up assessments will be conducted using a video link and conducted by a researcher with experience of working with marginalised young people.

The recruitment of MDFT therapists will be conducted through local organisations and aim to reflect the diversity of the population where it will be delivered. Young people will be able to choose a therapist who their own cultural or ethnic background or protected characteristics.

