Staff at Barnardo's will screen referrals to ensure they are consistent with the study inclusion and exclusion criteria and take informed consent. The principle of Gillick consent will be employed by staff trained in assessing Gillick competence to assess whether participants are mature and intelligent enough to make their own informed decisions. As a rule, young people aged 13 years or more, of average intelligence, are considered Gillick competent. Unless there is a specific reason not to do so, parents/ carers will be informed of the young person's participation in the study. Where consent cannot be taken using the Gillick principle, consent will be sought from a person with parental responsibility, in this scenario if a parent/ carer provides consent the young person will also have to provide assent to ensure there is no parental coercion to participate. Parent/carer consent is not required at the start of delivery. MDFT therapists will work with the young person to build their trust in the process and comfort with seeking parental/carer consent. They will also work to identify a trusted adult that could take the place of a parent/carer where needed. Broadly speaking, we would expect parents to be approached within a month of the young person starting MDFT. Giving young people the time and space to decide whether to approach a trusted adult, who it may be, and how they may approach them is crucial to the rapport building process.

It is anticipated that 60% of the referrals will come from Bristol and 40% from Newport, based on the relative population sizes. This means that 4 therapists will be recruited in Bristol and 3 in Newport. Based on our delivery in Bristol to young people being harmed in their communities through substance use, serious violence, and exploitation, we receive referrals showing a disproportionate percentage of racially minoritised young people. Following discussion with our referring partners in both LAs, we believe this pattern will be reflected in the MDFT pilot.

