On completion of assessment battery research staff receive automated message of a referral, randomisation conduct, allocation relayed back to Barnardo's staff who either initiate MDFT or make referral to BAU.

Randomised to BAU (200) Randomised to MDFT (200)

YP referred to alternative service YP allocated MDFT therapist

Outcome assessment at month 6 Outcome assessment at month 6 (n=182) (n=182)

Outcome assessment at month 12 Outcome assessment at month 12 (n=160) (n=160)

Data is collected at 6- and 12-months using bespoke, secure, on-line data collection system and transferred to secure servers managed by the University of Kent. Six- and 12-month data collection is completed by research staff blind to participant allocation and participants receive a payment of £25 for completing assessments at baseline 6- & 12 months.

Sample size calculations

Sample size estimation was conducted in STATA18. A clinically important effect size for substance use frequency in adolescents is estimated as 0.27, similar to the lower bound

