estimates found in systematic reviews of MDFT (Filges T. et al., 2018, van der Pol et al., 2017b). This equates to a number needed to treat of 6, where at least one in six participants receiving MDFT would show clinically important benefits, and a difference in the frequency of substance use of at least 13% in the MDFT group. Detecting an effect size smaller than this provides no additional benefit, the commissioning of services in England and Wales requires the service to achieve a clinically important difference for the target population. To detect this difference, with power at 80% and alpha of 0.05 and a two-tailed test, requires a sample of 480 participants followed-up at the 6-month endpoint. Using data from other studies of substance using adolescents (Coulton S et al., 2023, Deluca et al., 2020) we estimate the prepost-test correlation of the frequency of substance use to be 0.4, and incorporating this into the sample size calculation reduces the number followed-up to 364, 182 in each group. Assuming a loss to follow-up at the endpoint of 10%, similar to other studies in adolescent substance use populations (Coulton et al., 2024) inflates the number needed to randomise to 400. Assuming 80% of those eligible will be willing to consent an indication of acceptability of the study to participants and a lower figure than other studies in similar populations (Coulton et al., 2024) would mean we would need to approach 480 across both sites. Recruitment will be continuous between September 2025 and January 2027, 28 per month will need to be approached in total across both sites per month with the expectation that 24 will consent to participate in the trial across both sites. We anticipate. Based on relative population size that 40% of referrals will come from Newport and 60% from Bristol.

Table 2: Recruitment/ retention table

	Q1	Q2	Q3	Q4	Q5	Q6	Q7	Q8	Q9	Q10	Q11
Months (e.g. Oct-Dec 23):	May-Jul 25	Aug-Oct 25	Nov 25 - Jan 26	Feb - Apr 26	May-Jul 26	Aug-Oct 26	Nov 26 - Jan 27	Feb - Apr 27	May-Jul 27	Aug-Oct 27	Nov 27 - Jan 28
Target number of children and young people referred into the project	0	50	75	75	75	75	75	75	218	360	500
Target number of children and young people recruited to the project and evaluation	0	40	60	60	60	60	60	60	174	288	400
Target number of children and young people who withdraw/drop out	0	4	6	6	6	6	6	6	23	35	40

Table 3: Sample size calculations

		PARAMETER		
Minimum Detectable Effect Size (MDES)		0.27		

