Fractional regression analysis will be performed to model the relationship between prerandomisation factors, and demographics on observed outcomes at 6 months, for the primary outcome. Interaction terms with allocation arm will be included in the analysis, and a significance level of 0.1 will be used to determine which factors are to be included in the model. Pre-randomisation factors will include ethnicity, sex, age, IMD decile, severity of substance use, and baseline family cohesion, motivation, self-efficacy and expectancy. This analysis will be augmented by an additional analysis including participants in the intervention arm only using the same pre-randomisation factors but also including process measures of adherence, intervention fidelity, and therapeutic alliance.

Latent class approaches will be used to explore the hypothesised mechanism of change exploring changes over time in family cohesion, motivation to change, self-efficacy and substance use expectancy.

Qualitative analysis

The aim of the qualitative analysis in the efficacy study will be to link samples by grouping, comparing, and contrasting responses from all data sources to address the research questions. This linking of data allows for a concentrated and more meaningful analysis of the influence of the programme through its contexts and mechanisms, and of its perceived impact through a thematic blending of data elements. The key questions that we will seek to answer at this stage will include:

- Are there any residual or new external or logistical issues impacting referral, intervention delivery, or attrition?
- What are young peoples' positive and negative experiences of the intervention and how do these fit with providers' perceptions?
- At what points in the intervention have these experiences occurred?
- Are there practices associated with the intervention that can be amended to further increase its acceptability and impact?
- Do stakeholders see the intervention as impacting participant's behaviour?
- In what ways has substance use and offending been impacted?

This provides an opportunity to explore the perceptions of the intervention from the point of view of a variety of stakeholders using Normalisation Process theory (NPT; (Finch et al., 2012). Bracketing, reflexivity, and member checking will be employed to ensure trustworthiness and rigour.

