In both sites, as a Strategic Partner for both LAs, Barnardo's has the local relationships to ensure effective referral pathways are put in place. It has been agreed that referrals will primarily come through the Front Door of each LA as well as through both Youth Justice Teams. In Bristol, the new MACE (Multi-Agency Child Exploitation) arrangement, which has oversight of young people at risk and those being harmed through exploitation, will also act as a key referrer.

MDFT will be adapted for delivery in the UK context. Adaption follows the ADAPT guidance (Moore et al., 2021) to ensure the intervention that aims to maximise the efficacy by ensuring they fit well within a UK delivery context.

Staff recruitment will recruit a broad, culturally diverse range of therapists by advertising roles in community venues and within local community networks. Barnardo's training offer for all staff supports culturally sensitive delivery. Where possible, consideration will be given to matching the young person and therapist. This might be along lines of shared protected characteristics, interests and when the therapist has a particular skill set that will meet the young person's needs. As part of induction, all staff undertake an equality, diversity and inclusion course, which includes discussions around culturally sensitive delivery, unconscious bias and understanding the experience of children from different backgrounds. Learning and Development is supported by SEEN (https://weareseen.org.uk/), the national resource centre to improve outcomes for children and young people of African, Asian and Caribbean heritage. As part of the support offered to all staff through SEEN, there is a knowledge bank containing resources such as: 'An emancipatory approach to cultural competency: The application of critical race, postcolonial, and intersectionality theories', 'Anti-racist supervision (for professionals)' and 'Being Black in rural spaces (UK Youth)'.

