Young people consulted as part of this process raised concerns around engaging with therapists or researchers that were of different ethnicities or cultural backgrounds, as they felt that this may lead to a lack of understanding of the issues that they faced. This was highlighted by several young people from a variety of backgrounds. When the notion of training and education for all prospective staff was discussed, many of the young people expressed that this would help to form the trusting relationships required for such a process to work. They were however keen to point out that they felt using the phrase 'cultural competency' suggested that one could attain a level or 'certificate' in this area, when this was only something that would work with a sustained and ongoing interest and willingness to learn about the experiences of individuals from other ethnic and cultural backgrounds. This move away from the notion of 'cultural competency' is something that is echoed in relevant research literature (Fisher-Borne et al., 2015).

Mitigation: Data around those individuals who both do and do not engage or continue to engage will be collected throughout the project to be able to identify any trends within groups. Should it be necessary, the research team will explore any access needs (availability of further tailored resources etc.) that may be required moving forward. The intervention provider, Barnardo's has experience in recruiting, training and retaining interventionists who are representative of the ethnic diversity of the areas they serve.

As stated above, the introduction of culturally relevant and sensitive training to individuals on the research and delivery teams were welcomed by young people, but with the caveats described above.

	□ Positive impact □
Sex	☑ Negative impact
	□ No impact
	Narrative: Previous studies of MDFT have indicated that it is an
	effective treatment for substance use in both male and female participants (Greenbaum et al., 2015) and thus there is the likelihood of a positive impact in this regard.
	In the UK, female involvement in crime (particularly for young people) is still not as well understood as that of their male counterparts. Despite accounting for 13% of proven youth offenses is 2022, their involvement in violence remains largely invisible and support services are rarely specifically catered to girls and young women (Local Government Association, 2024).

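### If young people take up the offer of a therapist of their own background, therapist differences can load onto the exploratory ethnicity-by-arm test, whose model has no therapist term

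*Protocol*

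**What the plan says.** The Design section, under Impact evaluation, states: "Young people will be able to choose a therapist who their own cultural or ethnic background or protected characteristics" (a verb is missing in the source, but an offer of choice is clear). Appendix I, under Inputs, is softer: where possible, "consideration will be given to matching the young person and therapist", on protected characteristics, interests or skill set. The equality assessment in Appendix III explains why uptake is plausible, since those consulted "raised concerns around engaging with therapists or researchers that were of different ethnicities or cultural backgrounds". That remark is background only; it sets no matching rule, therapist number or test.

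On numbers, the Participants section says: "This means that 4 therapists will be recruited in Bristol and 3 in Newport". The progression criterion in Appendix II is also seven. Appendix I, under Inputs, gives a usual team of six to eight per site, which does not agree. The Business as usual section says that MDFT therapists do not deliver BAU.

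The Exploratory analysis section plans a fractional regression of the six-month primary outcome with factor-by-arm interactions and a 0.1 threshold for inclusion. "Pre-randomisation factors will include ethnicity, sex, age, IMD decile, severity of substance use" and four baseline psychological and family measures. Therapist is not listed. The companion MDFT-only model adds adherence, fidelity and alliance, again without therapist. A regression that includes the interventionist is planned under Implementation and process evaluation, but it is not linked to the ethnicity interaction. A multi-level model is mentioned under Efficacy study analysis for the secondary outcomes, with no levels named.

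**The concern.** When therapists are assigned without regard to ethnicity, each therapist sees both groups, and differences between therapists largely cancel from the ethnic contrast within the MDFT arm. When therapist is chosen on ethnicity, they no longer cancel. BAU has no MDFT therapists to offset them, so they fall on the ethnicity-by-arm term. A model without therapist treats participants as independent and reports a standard error that leaves this component out.

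This is distinct from therapist clustering in the overall MDFT-versus-BAU comparison. It is the link between therapist and ethnicity that disturbs the interaction test.

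Effects by ethnicity are a named question (ERQ12 and the Sub-group analyses section), and the exploratory model is meant to inform revision of the logic model (ERQ11). A finding that MDFT works better or worse for minoritised young people could partly reflect the few therapists who saw most of them.

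**Working it through.** **Plan's own sample size.** With effect size 0.27, correlation 0.4, 80% power and two-sided alpha 0.05, n per arm = 2 × (1.960 + 0.842)² × (1 − 0.4²) / 0.27² ≈ 181, or 362 in total. The protocol "reduces the number followed-up to 364, 182 in each group", so this reproduces, and 182 per arm is used below. The unadjusted 480 does not follow from the same inputs (they give 432), but it does not enter this check.

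**Inputs from the protocol:** 182 analysed per arm; 35% from racially minoritised groups (Participants), about 64 and 118 per arm; seven therapists, four and three by site, in the MDFT arm only; test level 0.10.

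**Assumed, because the protocol gives no values:** therapist ICC 0 to 0.10; two or three of the seven therapists from minoritised groups; no, half or full matching, applied within site and to both groups of young people; ethnicity as a single yes/no factor; no true ethnicity-by-arm effect; a linear model with robust standard errors in place of the fractional one.

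**Closed form, full matching, two therapists against five.** On the SD scale:

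- Variance the model sees: 2 × 0.84 × (1/63.7 + 1/118.3) = 0.0406, SE 0.20.
- Variance it omits: ICC × (1/2 + 1/5) = 0.7 × ICC.
- ICC 0.05: total 0.0406 + 0.035 = 0.0756, true SE 0.27. The effective critical value is 1.645 × √(0.0406/0.0756) = 1.21, giving about 23% false positives.
- ICC 0.02: total 0.0546, about 16%.
- ICC 0.10: total 0.1106, about 32%.

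**Simulation, 4,000 trials per setting.** The model has arm, ethnicity, their interaction, site and baseline, and no therapist term. False-positive rate (%) of the nominal 10% test:

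| Matching | Minoritised therapists | ICC 0 | ICC 0.02 | ICC 0.05 | ICC 0.10 |
|---|---|---|---|---|---|
| None | 2 of 7 | 10.5 | 10.1 | 10.2 | 10.6 |
| None | 3 of 7 | 10.7 | 10.4 | 11.6 | 10.6 |
| Half | 2 of 7 | 11.1 | 12.5 | 14.4 | 16.8 |
| Half | 3 of 7 | 10.1 | 11.8 | 13.2 | 16.6 |
| Full | 2 of 7 | 10.7 | 16.1 | 23.8 | 32.0 |
| Full | 3 of 7 | 10.2 | 14.6 | 20.8 | 30.0 |

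The simulation standard error near 10% is √(0.1 × 0.9/4000), about 0.5 points. The first two rows and the ICC 0 column are close to nominal, so both matching and therapist variance are needed for inflation.

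**If the team were larger.** Appendix I's six to eight per site would mean 12 to 16 in all. With, say, 14 therapists split 4 and 10, the omitted variance is ICC × (1/4 + 1/10) = 0.35 × ICC, half as large. At ICC 0.05 the total is 0.0406 + 0.0175 = 0.0581, and full matching gives about 17% instead of 23%. The problem shrinks but remains.

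**Effect of a therapist term.** In a linear refit with a therapist random effect in the MDFT arm only (2,000 trials per scenario), the false-positive rate was 11-14% with a normal reference and 5-8% with t on 5 degrees of freedom. With this few therapists the reference distribution matters. The remedy was not tested in the fractional model or the latent class analysis.

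**The case against.** The strongest objection is that a therapist term in an exploratory model is the kind of detail an SAP may supply, and the SAP is not shown. That is fair as to where the repair can be made. However, the protocol itself fixes the model type, the factor list and the threshold, and separately creates the link between therapist and ethnicity. The model as written is open to the problem.

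Second, a reader might infer that the ethnicity test is confounded and will flag false ethnic differences. The documents do not support that. Appendix I only considers matching, on several grounds besides ethnicity. Three or four therapists per site limit what can be matched. The minoritised share covers several groups, treated here as one. No ICC is given. The 32% figure is the extreme of the assumed range, not an expectation.

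Third, the 0.1 level is a screen across nine factors. If the tests were independent, at least one false inclusion would have probability 1 − 0.9⁹, about 61%, so one factor moving from 10% to 12-14% changes little overall. This stands against any strong claim. It does not remove the point, because ethnicity is singled out as a trial question and its estimate will be read on its own.

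Finally, therapist is not ignored altogether, given the process-evaluation regression on the interventionist. That analysis does not correct the ethnicity interaction.

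**Conclusion.** The point holds in conditional form. The protocol offers choice or matching by background, plans seven therapists in one arm, and tests ethnicity-by-arm without therapist. If therapists differ and matching is taken up, the estimate can carry therapist differences and its standard error is too small. For assumed ICCs of 0.02 to 0.10, the nominal 10% test runs at about 12-17% with half matching and 15-32% with full matching, and at about its nominal level if either condition is absent. These figures rest on the assumed ICC, uptake of matching and number of minoritised therapists, and on a linear stand-in for the fractional model.

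The analysis is exploratory. It should not be inferred that the primary result is threatened by this mechanism; it is not. The matter is worth correcting because the question is a named aim and the correction is cheap.

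**What to change.** - Leave the matching policy unchanged.
- In the ethnicity-by-arm analysis, allow for therapist in the MDFT arm with a partially nested random effect and small-sample inference. This can be the main exploratory model or a sensitivity analysis beside the fractional regression.
- Record, for every MDFT case, the delivering therapist and whether the pair was matched on ethnicity. Matching status should be captured prospectively.
- Tabulate therapist by ethnic group. Where one or two therapists treated most of a group, state that the ethnicity effect cannot be separated from therapist; a random effect widens the interval honestly but cannot separate them under near-complete matching. Apply the same caveat to the latent class findings on ethnicity (Sub-group analyses, ERQ12).
- Reconcile seven therapists in total (Participants, Appendix II) with six to eight per site (Appendix I).

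The cost is some analysis wording, one extra yes/no field and one table. The downside is a wider interval for an exploratory contrast that already has limited power.
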